6. SAFETY ASSESSMENTS AND MONITORING

6.1 Specification of Safety Parameters

All individuals eligible for participation have single ventricle physiology and are recognized to be at risk for exercise intolerance, declining ventricular function, and arrhythmias. The small increased risk to study participation is described in detail in Section 11. Any complication during a study evaluation or change in function occurring within 24 hours of a study evaluation, will be considered an adverse event and reported as described below.

6.2 Recording and Reporting Adverse Events

This study is not an intervention study. However, a major component of safety monitoring is ascertainment and reporting of adverse events (AE), including adverse reactions to study procedures. The approach to these activities for this study is summarized in the sections that follow.

6.2.1 Definitions of Adverse Event, Suspected Adverse Reaction and Adverse Reaction

For the purposes of this study, adverse events will include any untoward event that occurs to the child participant during or within 24 hours of any study-related evaluation including the CMR, echo, ramped cycle exercise test or battery of neurodevelopmental assessments.

6.2.2. Classification of Adverse Events

Monitoring AEs requires that they be classified as to seriousness, expectedness, and potential relationship to the study, of which drive the reporting process.

a. Seriousness

A serious adverse event (SAE) is one that:

- Results in death,
- Is life-threatening (the subject was, in the view of the PI, in immediate danger of death from the event as it occurred),
- Requires inpatient hospitalization or prolongation of existing hospitalization,
- Results in persistent or significant incapacity or substantial disruption of the ability to conduct normal life functions, or
- Is an important medical event that may jeopardize the subject or may require medical/surgical intervention to prevent one of the serious adverse event outcomes.

The Common Terminology Criteria for Adverse Events (CTCAE) Version 4.0 MedDRA 12.1 (<http://ctep.cancer.gov>) provides a grading system that is used to categorize the severity of adverse events, as follows:

Grade 1	Mild	transient, requires no special treatment or intervention, does not interfere with daily activities
Grade 2	Moderate	alleviated with simple treatments, may limit daily activities
Grade 3	Severe	requires therapeutic intervention and interrupts daily activities
Grade 4	Life-threatening Or disabling	
Grade 5	Death	

A SAE, as defined above, encompasses CTCAE grades 4 and 5, and any Grade 3 event that requires or prolongs hospitalization, or that substantially disrupts the ability of the subject to conduct normal life functions.

b. Expectedness

The purpose of reporting is to provide new, important information on serious reactions or events previously unobserved or undocumented. Therefore, all AEs will be evaluated as to whether their occurrence was unexpected, using the following definitions:

- *Unexpected*: An unexpected AE or adverse reaction is one for which the nature or severity is not consistent with information in the protocol, or consent form. An AE or adverse reaction also may be categorized as unexpected if the event has not previously been observed at the same specificity and/or severity.
- *Expected*: An event is considered expected if it is known to be associated with the particular evaluation. Expected adverse events could include 1) falling from the bicycle exercise test, 2) developing an arrhythmia during exercise testing, 3) anxiety during the CMR, and 4) frustration at the time of the neurodevelopmental testing.

c. Causality

Causality assessment is required to determine which events require expedited reporting. The following criteria will be used to determine causality:

- *Not Related*: The event is clearly related to other factors, such as the subject's clinical state, or non-study drugs or interventions.
- *Possibly Related*: The event follows a compatible temporal sequence from the time of study evaluation, but could have been produced by other factors such as the subject's clinical state or non-study drugs or interventions.
- *Probably Related*: The event follows a reasonable temporal sequence from the time of study evaluation, and cannot be reasonably explained by other factors such as the subject's clinical state, or non-study drugs or interventions.

6.2.3. Identification and Data Collection Procedures

AEs that are not considered adverse reactions or suspected adverse reactions will be identified when they are reported to the clinical center or during scheduled study visits by study coordinators and investigators. AEs will be assessed using self-report, physical examination data, and medical record review.

6.2.4. Reporting Procedures (Table 3)

Fatal or life-threatening AEs are to be reported to the Data Coordinating Center (DCC) within 24-hours of first knowledge of the event. Those that are unexpected and considered possibly, probably, or definitely related to the study will be reported by the DCC to the Data Safety and Monitoring Board (DSMB) Chair, the Medical Monitor (MM), the National Heart, Lung, and Blood Institute (NHLBI), and all study Investigators as soon as possible, but no later than 7 calendar days after first knowledge of the event, followed by a complete report within 15 calendar days. All other fatal or life threatening events that are unrelated to the study will be reported semiannually to the DSMB and the NHLBI.

All other *SAEs* (*i.e.*, *non-fatal or not life-threatening*) that are unexpected and considered possibly, probably, or definitely related to the study will be reported to the DCC within 24-hours of learning of the event. The DCC will report the event to the NHLBI, DSMB and all study Investigators within 15 calendar days after first knowledge of the event.

All other *AEs* not meeting the criteria for expedited reporting will be reported to the DCC within 7 calendar days of first knowledge of the event. The DCC will report these AEs quarterly to NHLBI.

Table 3. Reporting of Adverse Events

Seriousness	Reporting Timeframe
Fatal or life threatening	Within 24-hours of learning of the event
Serious, but not fatal or life threatening, and pregnancy	Within 24-hours of learning of the event
All other	Within 7 calendar days of learning of the event

6.2.5. Reporting Adverse Events to Institutional Review Boards (IRB) for National Institutes of Health (NIH)-Supported Multi-Center Clinical Trials

The site Investigator or designee is responsible for reporting all serious adverse events to the local IRB in accordance with local policies and procedures.

6.2.6. Follow-up of Subjects after Adverse Events

For AEs with a causal relationship to the study conduct, follow-up by the PI is required until the event or its sequelae resolve or stabilize at a level acceptable to the PI.

6.3 Safety Monitoring

The Data and Safety Monitoring Plan for this trial will follow standard PHN monitoring principles. Oversight of data and safety is provided by the PHN DSMB, appointed by NHLBI. The DSMB meets at least twice a year to review data on AEs, adverse reactions, suspected adverse reactions, patient-reported outcomes, data quality, and study recruitment at regular intervals, and makes recommendations about study conduct to the Director, NHLBI.

The DSMB and NHLBI are assisted by a MM in reviewing serious adverse events in PHN studies. The PHN MM is the NHLBI's designee for determining causality and expectedness of all SAEs.

7. STATISTICS

7.1 Analysis Plan

The surviving participants and non-participants will be compared to assess representativeness of the SVR III cohort. The primary comparison of outcomes between shunt types will be performed according to the intention-to-treat principle. Secondary analyses of each aim will be performed using non-intention to treat, defined as the shunt in place at the end of the Norwood operation.

7.1.1. Analysis of the Primary outcome for Primary Aim: *To compare cardiac function at 11 years of age between subjects randomized to receive either of a RVPAS vs. a MBTS at the time of the Norwood operation*

RVEF as measured by CMR is the primary outcome for this study. Descriptive statistics will be presented across all patients and by randomized shunt type. Distribution of the RVEF will be examined with histogram and compared by shunt type with either a Student's t-test or a Wilcoxon rank sum test as appropriate. If the distribution of RVEF is found to be skewed or otherwise non-normal, non-parametric tools will be used or RVEF will be transformed appropriately to obtain a close to normal distribution.

7.1.2. Analyses of Secondary Outcomes

7.1.2.a Additional Measures of the Primary Aim

For all additional CMR and echo measures related to Aim 1, the distribution of each measure will be assessed. Continuous measures will be compared between randomized shunt types with either a Student's t-test or a Wilcoxon rank sum test as appropriate. Categorical measures will be compared with a Fisher exact test, Chi-square test or the Mantel-Haenszel test for trend.

In addition, subjects with CMR and echo performed within a 6 month window without an intervening cardiac procedure will be selected to assess the agreement between the two techniques. The continuous measures will be compared using Bland-Altman limits of agreement and Pearson's correlation coefficient. The Kappa statistic will be used to evaluate the agreement in the categorical measures in Echo and CMR.

7.1.2.b Secondary Aim 1: To compare the long-term death/transplant rates of subjects randomized to receive either a RVPAS vs a MBTS

Transplant-free survival rate will be calculated using the Kaplan-Meier method. The logrank test will be performed to determine if time since randomization to the composite endpoint of death or transplantation is different between the two shunt types. Cox proportional hazard regression will be used to model the time to death or transplant by shunt type; to determine if the shunt difference varies by time and to identify risk factors of the endpoint.

In addition, nonparametric competing-risks methodology will be used to estimate the cumulative incidence rate of death and transplant. Proportional subdistribution hazards model will be fit to assess the effect of covariate on death and transplant in a competing risk setting.

7.1.2.c Secondary Aim 2: To compare exercise tolerance between those randomized to receive a RVPAS vs a MBTS

VO₂ max, work rate VAT and items 4-11 from section 4.3.2.b, from ramped cycle ergometry will be compared between the two shunt groups. The distribution of the variable will be determined with descriptive statistics. If the variable is normally distributed, Student's t-test will be used to compare shunt groups. If non-parametric, then Wilcoxon Rank-Sum will be used.

7.1.2.d Secondary Aim 3: To compare the incidence of atrial and ventricular arrhythmias between those randomized to receive a RVPAS vs a MBTS at the time of the Norwood operation

Arrhythmias will be classified as atrial tachyarrhythmias or ventricular tachyarrhythmias. The rate of atrial and of ventricular tachyarrhythmias will be compared between the shunt groups with the Fisher exact test.

7.1.2.e Secondary Aim 4: To compare neurodevelopmental outcomes at 11 years of age in subjects randomized to a RVPAS vs MBTS

Descriptive statistics will be performed for each scale included in the ND battery. Student's t-test will be used to compare normally distributed measures, Wilcoxon Rank-Sum for non-parametric continuous measures and Fisher exact test for all dichotomous measures. Adjustment will be included for measures of socioeconomic status.

7.1.2.f Secondary Aim 5: To determine if early perioperative events other than type of systemic to pulmonary artery shunt are related to long-term outcomes

To determine if early events after the Norwood operation are related to long-term outcomes, comprehensive models will be explored for each of the primary outcome measures for each aim (RVEF by CMR, transplant-free survival at 11 years, VO₂ max at ramped cycle ergometry, incident atrial tachyarrhythmias, incident ventricular tachyarrhythmias, Wechsler full scale IQ, and Language and Math Achievement Tests). Candidate predictors for these models will include previously collected early events and additional medical and surgical variables since the last SVR/SVR II contact.

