2.2 Secondary Aims

Secondary Aim 1: To compare the long-term effect of the RVPAS to that of the MBTS on the incidence of death or cardiac transplantation in children with hypoplastic left heart syndrome (HLHS) and other single RV anomalies undergoing the Norwood procedure.

Hypothesis: The incidence of death or cardiac transplant will be higher in the RVPAS group compared to the MBTS group.

Outcomes:

- The composite of the earliest occurrence of mortality and cardiac transplantation using all available follow-up (ranging from 10 to 15 years).
- Conditional freedom from death or cardiac transplantation by 11 years among subjects who survived >1 year post-randomization.
- Survival at 11 years post-randomization and when the last enrolled subject is 11 years old.
- Transplant at 11 years post-randomization and when the last enrolled subject is 11 years old.
- The composite of the earliest occurrence of mortality, cardiac transplantation and pacemaker placement, using all available follow-up (ranging from 10 to 15 years).

Secondary Aim 2: To compare exercise tolerance between those randomized to receive a RVPAS vs. a MBTS at the time of the Norwood operation.

Hypothesis: Subjects assigned to the RVPAS group will have lower exercise performance at age 11 years compared to those assigned to the MBTS group.

Outcomes:

- Exercise capacity: Maximal Oxygen Consumption (VO₂max), maximal work rate, and anaerobic threshold

Secondary Aim 3: To compare the incidence of arrhythmias between those randomized to receive a RVPAS vs. a MBTS at the time of the Norwood operation.

Hypothesis: The RVPAS will be associated with a greater prevalence of ventricular arrhythmias, but will not differ from the MBTS in the prevalence of atrial arrhythmias.

Outcomes:

- History of ventricular arrhythmias by age 11 years by parent report and with medical record confirmation.
- History of atrial arrhythmia by age 11 years, including intra-atrial reentrant tachycardia (IART) or supraventricular tachycardia (SVT), by parent report and with medical record confirmation

Secondary Aim 4: To compare neurodevelopmental outcomes at 11 years of age in subjects randomized to a RVPAS vs. MBTS at the time of the Norwood operation.

Hypothesis: Impaired neurodevelopment will not be associated with Norwood shunt type but mean scores will be lower in single ventricle patients compared to the normative population.

Outcomes:

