- Achievement, as measured by the Wechsler Individual Achievement Tests (WIAT) (Math and Reading)
- Intelligence, as measured by the Wechsler Intelligence Scale for Children (WISC)
- Other domains of neurodevelopmental function including assessment of language, executive function, visual spatial skills, motor function, memory, social skills, behavior, health-related quality of life (HRQoL) and adaptive function.

Secondary Aim 5: To develop risk stratification models for the following classes of long term outcomes: 1) cardiac outcomes, 2) transplant-free survival, and 3) neurodevelopmental outcomes.

Hypothesis: Long-term outcomes at 11 years will be worse for participants with a higher frequency of medical events.

Analyses for this aim will:

- Provide information about the association of events and interventions other than the randomized surgical procedure with late outcomes.
- Identify early cardiac and neurodevelopmental surrogate endpoints that might be useful in future studies of management strategies.
- Determine if correlates of long-term outcomes vary according to patient subgroup factors.

Secondary Aim 6: To collect specimens from subjects with HLHS and other single RV anomalies and their parents in whom DNA samples either were not collected previously or are of insufficient quality or quantity, to further develop the biologic specimen repository (biorepository).

Purpose: *To build on the collection of genetic material from the SVR cohort, to leverage the careful phenotyping of the SVR cohort to provide an opportunity for future phenotype-genotype studies and to make samples available for future hypothesis-driven studies aimed at identifying genetic determinants of outcome in HLHS and related single RV lesions.*

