3.2 Prior Studies

The Single Ventricle Reconstruction (SVR) trial was the first multicenter, randomized clinical trial to compare two operations in the field of congenital heart disease.^{8,11} Children with HLHS and other related single RV lesions were enrolled and randomized to receive either a MBTS or a RVPAS at the time of the initial Norwood procedure. This landmark study provided extraordinary insight not only into the consequences of both shunt types, but also into the course, treatment responses and short- and mid-term outcomes for these medically complex patients. Through the SVR Trial and SVR Extension Study (SVR II), outcomes, including but not limited to the primary outcome of transplant-free survival, have now been evaluated in this patient cohort when the last enrolled patient reached 12 months and again at 3 years of age. While early post-operative transplant-free survival during the interstage period⁷ and at one year⁸ was better for those children randomized to a RVPAS, survival by the 3-year evaluation appeared equivalent between the two shunt types. Moreover, RVEF was somewhat diminished and the number of interventions was higher in the RVPAS group.¹² These findings raised concern that the RV dysfunction in the RVPAS group may be progressive, leading to significantly worse long-term outcomes; if so, the benefits of the RVPAS for short-term survival may be outweighed by longer-term morbidity and mortality. Thus, the optimal surgical approach for newborns with HLHS and related single RV lesions remains unclear.

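### For death and transplant as separate events, Section 7.1.2.b plans only a subdistribution hazards regression, which cannot separate an effect on the transplant rate from an effect on surviving long enough to be transplanted

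*Combined protocol and SAP*

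**What the plan says.** Section 7.1.2.b (Secondary Aim 1) has two layers.

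- **Composite.** Kaplan-Meier estimates are followed by a logrank test of whether "time since randomization to the composite endpoint of death or transplantation is different between the two shunt types". Then "Cox proportional hazard regression will be used to model the time to death or transplant by shunt type", and this model also serves to look for a time-varying shunt difference and for risk factors.
- **Separate events.** As an addition, "nonparametric competing-risks methodology will be used to estimate the cumulative incidence rate of death and transplant", followed by the regression: "Proportional subdistribution hazards model will be fit to assess the effect of covariate on death and transplant in a competing risk setting".

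No Cox model is named for one event with the other censored. The plan does not say how a subdistribution hazard ratio will be interpreted.

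Three other places bear on the point.

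- Section 2.2 lists survival and transplant as separate outcomes at fixed times, for example "Transplant at 11 years post-randomization and when the last enrolled subject is 11 years old".
- Secondary Aim 5 is "To develop risk stratification models for the following classes of long term outcomes: 1) cardiac outcomes, 2) transplant-free survival, and 3) neurodevelopmental outcomes", so its survival endpoint is the composite. Section 7.1.2.f agrees.
- Section 3.2 reports that early transplant-free survival "was better for those children randomized to a RVPAS, survival by the 3-year evaluation appeared equivalent between the two shunt types".

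**The concern.** The subdistribution model keeps children who have died in the risk set for transplant. Its hazard ratio therefore mixes two things: how often living children are transplanted, and how many children live long enough to be transplanted. A factor that raises early death lowers the transplant subdistribution hazard even if it has no influence on transplant in the living, and a factor that lowers early death raises it.

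This cohort is exposed to the effect because death is much the commoner event, and because the candidate covariates in Section 4.3.3 (neonatal shock, ECMO, cardiac arrest, genetic syndrome, birth weight) are ones that may act on early death. If the coefficient were read as an effect on the transplant rate, a marker of severe early illness could look protective against transplant. The background in Section 3.2 is partly about mechanism, namely whether ventricular dysfunction after the RVPAS progresses. For transplant, that question concerns the rate among living children, and none of the planned component analyses isolates it.

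**Working it through.** **Inputs from the documents.** Section 7.2: 549 randomised, 334 alive and transplant-free, so up to 549 − 334 = 215 composite events. Section 5.4: 352 alive in June 2014, of whom 18 had been transplanted, so up to 549 − 352 = 197 deaths. Deaths after transplant are not given. Section 3.2: the shunts differed early and appeared equivalent by 3 years. No rates by arm are given, and the early difference is not split into death and transplant.

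**The plan's own figure.** Section 7.3 states about 80% power for the composite at a hazard ratio of 0.67, with 50% versus 63% transplant-free.

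- ln(0.63)/ln(0.50) = 0.667, which agrees.
- Schoenfeld events for 80% power: 4 × (1.960 + 0.842)² / (ln 0.67)² = 196.
- Expected events: 549 × (0.50 + 0.37)/2 = 239, giving 87% power before allowances.
- The stated 80% follows if loss and crossover cost about 18% of events (1 − 196/239). Those rates are not given, so the figure is consistent but cannot be checked exactly. It is not in dispute here.

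**Why the ratio moves.** Write λ(t) for the cause-specific transplant hazard, S(t) for the probability of being alive and transplant-free, and F(t) for the cumulative incidence of transplant. The subdistribution hazard is

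λ(t) × S(t) / (1 − F(t)).

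If λ is the same in both groups and transplant is rare, the ratio between groups is roughly the ratio of their survival from death. Once first-year deaths have occurred:

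- 20% versus 50% early death: 0.50/0.80 = 0.625
- 5-point gap: 0.725/0.675 = 1.07
- 10-point gap: 0.75/0.65 = 1.15
- 15-point gap: 0.775/0.625 = 1.24

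**Simulation.** Hazards were piecewise exponential with cut points at 1, 3 and 11 years, and the transplant hazard was equal in both groups. The following are assumptions: the early death rates, a transplant hazard of 0.002 to 0.012 per year (about 22 to 45 transplants in 548 children), two equal groups, no loss to follow-up, and independent event times. Hazard ratios come from 2,000,000 subjects, and rejection rates at two-sided 5% from 1,500 trials of 548.

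| Scenario (true cause-specific transplant HR 1.00) | Subdistribution HR, transplant | Subdistribution test rejects |
|---|---|---|
| No effect on death | 0.99–1.01 | 3.7–5.5% |
| 5-point early gap, persists | 1.07–1.08 | 3.5–5.9% |
| 10-point early gap, persists | 1.14–1.15 | 5.3–5.9% |
| 15-point early gap, persists | 1.23–1.24 | 6.6–9.3% |
| 10-point early gap, closed by about 3 years | 1.02–1.03 | 3.9–5.2% |
| Risk factor, 20% vs 50% early death | 0.62–0.64 | 15.1–29.3% |

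The cause-specific Cox model gave 0.99 to 1.01 in every row and rejected 3.0 to 6.0% of the time. Simulation error near 5% is about √(0.05 × 0.95/1500) = 0.6 percentage points.

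The closing-gap row used survival from death of 65% versus 75% at 1 year, 63% versus 64% at 3 years, and 60% in both groups at 11 years. The survival ratio falls from 1.15 to 0.64/0.63 = 1.02 and then to 1.00. The subdistribution effect is therefore not proportional over time in that row, although the cause-specific transplant effect is constant at 1.

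**The case against.** The strongest reply is that the subdistribution hazard ratio is not wrong. It is a valid effect on cumulative incidence. Transplant by 11 years is a cumulative-incidence quantity, and the plan pairs the model with cumulative incidence estimates. If more children in one arm live to be transplanted, transplant incidence in that arm really is higher, and under randomisation that is a legitimate total effect. This stands. The 15 to 29% rejection rates in the last row of the table reflect a real difference in incidence. They mislead only if read as an effect on the rate in living children.

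A reader might also infer that the RVPAS is bound to show a spurious increase in transplant. The documents do not support that. Section 3.2 goes on to say that survival appeared equivalent by 3 years. With a gap that closes, the ratio is about 1.02 to 1.03 and rejection stays near 5%. Larger values for shunt need an early gap that persists, and even a persisting 10-point gap gives 5 to 6% rejection with so few transplants.

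Finally, the lead analyses and the Aim 5 survival endpoint use the composite, which is unaffected, and cumulative incidence of both events will be shown, so an early-death effect would be visible. That is true, but the curves are not adjusted for covariates and do not separate the two pathways. Nor should every statement of effect rest on cause-specific models. A cause-specific transplant ratio conditions on children still alive, which is a selection after randomisation, and it does not answer the question of transplant by 11 years. The two models answer different questions.

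**Conclusion.** The gap is real but limited to the component models in Section 7.1.2.b. With only a subdistribution regression, the study cannot tell a covariate that changes the transplant rate from one that changes survival to transplant. The size matters for strong early-death risk factors: a subdistribution ratio of 0.62 to 0.64 with no effect on the rate, under an assumed 20% versus 50% early death and a factor present in half the cohort. For shunt it is likely small, 1.02 to 1.03 if the gap closed by 3 years. All these sizes rest on assumed death rates and transplant hazards, not on trial figures. No primary or composite conclusion changes. The point is an inexpensive improvement to the plan and does not invalidate any planned analysis.

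**What to change.** In Section 7.1.2.b:

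1. Add cause-specific Cox models for death before transplant (censored at transplant) and for transplant (censored at death), by randomised shunt and for the covariate analyses.
2. Report them beside the subdistribution models and cumulative incidence curves already planned, always for both events.
3. State the reading in advance: the subdistribution hazard ratio is an effect on cumulative incidence, and the cause-specific hazard ratio is an effect on the event rate among children still alive and transplant-free.
4. Check proportionality of the shunt effect in both kinds of model. The plan now looks for a time-varying shunt effect only in the composite Cox model.

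The cost is a few sentences of plan wording, two standard models on data already being collected, and somewhat longer tables. Section 7.6 already provides for recording the change in a revised statistical plan.
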